Surveys with clinics, project implementers and participants will be conducted. We will administer an organizational readiness survey in all clinics in the standard and community-engaged arms. All clinic staff involved in the implementation of the pay-it-forward intervention will be encouraged to take the survey which will assess the motivation and capabilities of their clinic. Every month, at each site in the standard and community-engaged arms, a member of the research staff will assess the extent to which pay-it-forward is implemented in accordance with the protocol using a fidelity checklist. This checklist will document how often each step of the Pay-it-forward protocol (including screening, consent, explanation of study procedures and Pay-it-forward, sample collection, donation, and

community engagement activities) is implemented. Research staff will also document the sequence of the study procedures, site-specific adaptations, and any implementation challenges that occur at each site visit.

Qualitative interviews

MSM, healthcare providers, and PIONEER organizers will be recruited for in-depth interviews. We will recruit MSM in the clinic, immediately following participation in the RCT. We will also recruit, and interview selected health professionals to explore their perspectives about generosity in clinical settings to contribute to the development of more generous health services and inform clinical innovations. Purposive sampling strategies will be used to recruit MSM involved in each implementation strategy arm, those who participate and those who do not, those who provide a higher donation and lower donation, and healthcare providers. Among organizers, we will recruit them by sending a text message to a purposive sampling of organizers. This will include those at MSM-led clinics and public clinics, organizers who identify as gay and those who do not, and other key characteristics. We will develop a topic guide to guide the MSM and healthcare provider interviews based on the literature review, fieldnotes and reflections during the implementation of RCT. Main topics will include the following: (1) reasons for getting tested; (2) understanding and perception of the pay-it-forward concept; (3) specific questions about emotions of gratitude after receiving a test that is supported by another community member; and (4) self-identity in the MSM community and level of integration within a community; (5) intention and motivation to initiating and mediating helping behaviors within the community. The healthcare provider interviews will explore their perceptions of the factors affecting generosity will be explored at both individual and collective levels, particularly in terms of cynicism and gratitude within the practitioner-patient relationship. Analysis will focus on how generosity may be demonstrated and received, expanded and restricted, and its impact on patient recipients, colleagues and the clinical settings, and implications for the wider social community beyond the clinic space. We will obtain a recorded verbal informed consent from all interviewees before the commencement of the interview. Interviews will last about one hour and will take place either in person or over the phone-based on participant preference.

Interviews will be audio-recorded and personal information will not be recorded. Unintentional recording of personal information will otherwise be redacted before transcription. Each participant will receive a small monetary incentive of ¥50 (7.50 USD) for their participation. All recorded interviews will be transcribed, and transcripts will be checked by one research staff member. Summaries of interviews will be written up for preliminary data analysis. In addition, we will collect anonymized text from handwritten postcards and other community engagement activities.

Sample size and power considerations

A total of 25 MSM participants, 27 healthcare providers, and 25 PIONEER organizers will be

recruited for individual interviews. Enrollment will cease when no new themes and sub-themes emerge, inferring data saturation. All eight participating clinics that are implementing the pay-it-forward intervention (both standard strategy and community-engaged strategy) will be invited to respond to questions related to implementing the intervention (see Table 3). All participating clinics will be invited to answer questions related to organizational implementation and maintenance. Operational definitions and example measures of the five dimensions of RE-AIM adapted for the study are shown in Table 3.

Outcome measures

The outcomes will include (1) primary RE-AIM data comparing differences between the community-engaged pay-it-forward strategy and the standard pay-it-forward strategy; and (2) qualitative data describing mechanisms related to test uptake and donation decisions, respectively.

Data analysis

Thematic analysis will be used to analyze qualitative data. A codebook will be developed by a senior qualitative researcher. Two research assistants will then code the transcripts based on the codebook. NVivo version 12 (NVivo, Columbus, OH) will be used for qualitative data analysis. Descriptive data analyses, independent sample t-tests and chi-square tests will be used to compare differences in RE-AIM measures between pay-it-forward and standard-of-care arms. We will generate a global implementation score and scores of separate dimensions and convert them to a z-score. Correlates of global implementation and implementation dimensions will be examined using general linear mixed models (GLMM). In addition, qualitative data on social networks will be applied to disentangle the connection between an individual's gratitude and position within a network comprised of helping relationships (both direct and indirect relationships). Finally, we will use linguistic inquiry word count to analyze textual information gathered as part of community engagement activities.

Safety management plan

Criteria for withdrawal: if participants want to quit the study for any reason. Project implementers will do data and safety monitoring.

Data management information

For the surveys and demographic questionnaires, all data are directly entered into computers at the UNC Project China office as participants complete the surveys. Programs to ensure accuracy, completeness, and internal consistency are automated. Data can be readily downloaded and converted to the format of commercially available statistical software. During the collection of the online portion of the study, all data will be transmitted securely using SSL (TLS) 128-bit encryption across the Internet (HTTP). SSL provides users with the assurance of access to a valid, "non-spoofed" site, and prevents data interception or tampering with sensitive information. The SSL certificate that will be used for this project will

use 128-bit encryption, the preferred security level of government and financial institutions. 128-bit encryption offers protection that is virtually unbreakable. For example, if a hacker could crack a standard 40-bit SSL session in a day, it is estimated that it would take well beyond a trillion years to accomplish the same thing against a 128-bit SSL session. A dedicated server, which eliminates security issues involved with shared hosting environments where hundreds of websites and users reside on one shared web server as well as ensuring both physical and network security, will be used to house the data. Data will then be stored in a secured server at Dermatology Hospital, Southern Medical University. The server will be configured with a redundant hard drive array to ensure reliability. Access to the data will be password-protected within the server's firewall. Only the PI and a designated senior staff member will have the password to access the "key" that links the non-descript identifier to personally identifiable information. IP addresses of participant's computers will not be collected at any time. Cookies will not be used in any way to track participant activity. A quick link will exist on each survey page to provide participants with a rapid way to switch to an innocuous website if their privacy is interrupted while completing the survey.

For participants' urine testing results and clinical outcomes, the data will be recorded directly and input into the Health Information System (HIS) at the public STD clinic. Data will be downloaded and stored the same way as the survey data.

Table 3. Dimensions of RE-AIM in implementation research adapted for pay-it-forward.³¹

Dimensions	Level	Operational definitions	Measurement method	Analysis
Reach	Individual	
 Proportion of MSM who enter the clinic and are screened for eligibility Percent of MSMs who visit the clinic compared to the MSM in the catchment area 	RCT data Local CDC data	Descriptive analysis
Effectiveness	Individual	
 How effective are the two implementation strategies in promoting gonorrhea test uptake? Does pay-it-forward influence secondary outcomes (chlamydia testing, treatment and prevention outcomes)? 	RCT data	Covered in RCT analyses above
Adoption	Organizational	
 Is the organization ready to adopt pay-it-forward? 	ORIC survey – administer after piloting and again early during RCT Qualitative interviews	Descriptive analysis Rapid or content analysis
Implementation	Organizational	
 Fidelity: what is the extent to which local staff implement the pay-it-forward according to the SOP and how does this 	Fidelity checklist filled out by research staff member observing intervention	Descriptive analysis T-test/regression for fidelity score and/or adaptations vs intervention effectiveness Time series of adaptation

		
impact effectiveness?
 
 Adaptations: what adaptions are implemented and how do they impact effectiveness? 	
Documentation of adaptation content and timing
 
Interviews with clinic staff
	
implementation
 
Rapid or content analysis

Maintenance	Organizational	
 Donations over time during the intervention Cost-effectiveness What are the barriers and facilitators of maintenance? What do implementing partners need to sustain Pay-it-forward? 	
Donation and costing data
 
Qualitative interviews
	
Descriptive analysis
 
Time series
 
Cost-effectiveness analysis
 
Rapid or content analysis

Discussion

Pay-it-forward is a novel behavioral and financial model. Our previous studies showed that it is cost-effective, but the study findings have limited representativeness due to the primary involvement of MSM-led clinics but an exclusion of public clinics, which are the major provider of STD testing and treatment services in the Chinese setting. There is also a lack of understanding of the implementation process and a missed opportunity to optimize the implementation strategy. By enhancing the community engagement components of the strategy, our trial aims to test the effectiveness of an enhanced pay-it-forward implementation strategy in comparison to the standard pay-it-forward approach and a control arm. We propose a programmatic cluster RCT to document high-quality evidence on the effectiveness of different pay-it-forward implementation strategies and to better understand the real-world practices. The proposed study will provide an evidence base on whether community-engaged pay-it-forward implementation can strengthen the effectiveness and inform future expansion of pay-it-forward intervention strategies to improve gonorrhea testing and treatment for MSM in diverse clinic settings in China.

This study has important implications for evidence-based practices for delivering important but underfunded public health services in a novel and efficient way. Hybrid implementation study designs focus not only on effectiveness but also on assessing implementation outcomes. Generating evidence on the implementation itself will inform evidence-based practices and enable us to tap into the potential of normalizing or integrating the pay-it-forward interventions into existing programs to promote gonorrhea testing among a key community. Our hybrid implementation-effectiveness design has a primary focus on testing two pay-it-forward implementation strategies as well as evaluating other domains, including reach, adoption, implementation, and maintenance. These will help inform what is possible in routine practices, translate research findings into practices and scale up the strategy in gonorrhea testing service delivery and beyond.

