Methods: PIONEER will be a three-arm, programmatic cluster randomized controlled trial (RCT) to compare the effectiveness of the three implementation strategies, followed by a mixed-methods implementation evaluation study guided by a transformative paradigm. For the cluster RCT, we will enroll 12 diverse clinics, which will be randomly assigned to one of the intervention arms for delivering gonorrhea testing: a standard pay-it-forward implementation strategy with minimal encouragement to get tested, a community-engaged pay-it-forward strategy, and a control arm in which men pay for their own STD test. The public and MSM-led clinics in the same city will be randomized to the same study group to prevent contamination. The primary outcome of the RCT will be gonorrhea test uptake, and secondary outcomes will include chlamydia testing, STD treatment among those with infection, amount donated, 100% condom use, and antimicrobial resistance. A sequential explanatory mixed methods design will be used to evaluate the implementation process. Data sources will include survey data on the acceptability of the intervention, intervention appropriateness, feelings and attitudes towards the interventions among participants, administrative data about test uptake, treatment rate, and donations, as well as qualitative data to gain insights about men's perceptions and attitudes towards the pay-it-forward interventions strategies, mechanisms driving uptake and donating behaviors. Both survey and qualitative interviews with implementers and organizers about fidelity and adherence to protocol, intention to continue and maintain a pay-it-forward intervention, and barriers and facilitators of implementing the intervention will be conducted.

Discussion: PIONEER will substantially increase gonorrhea testing among MSM in China, providing an innovative new financial mechanism to sustain STD screening among sexual minorities in low- and middle-income countries. This study will answer compelling scientific questions about how best to implement pay-it-forward and the individual and organizational characteristics that moderate it.

Contributions to the literature

- This cluster randomized controlled trial aims to examine the effectiveness of two implementation strategies involving different levels of community engagement to translate the generosity created by the pay-it-forward approach into test-taking action.

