Our trial will use a hybrid effectiveness-implementation study design which values both

intervention effectiveness and implementation process. Specifically, the PIONEER trial will be a three-arm, programmatic cluster randomized controlled trial (RCT), followed by a mixed-methods implementation evaluation study. The cluster RCT aims to compare the effectiveness of the three implementation strategies, and the implementation evaluation will look into other domains of the implementation process guided by the RE-AIM framework.

For the cluster RCT, we will enroll 12 diverse clinics (i.e., MSM-led and public sexual health clinics), and the clinics will be randomly assigned to one of the intervention arms for delivering gonorrhea testing: a standard pay-it-forward implementation strategy with minimal encouragement to get tested, a community-engaged pay-it-forward strategy, and a control arm in which men pay for their own STD test. Randomization will be based city economic status and stratified by clinic type. The standard strategy, which was developed through our previous pay-it-forward research, will have men who enter the clinic be provided with a free gonorrhea test and shown handwritten postcards from other MSM in the local community. The community-engaged strategy will include all elements of the standard strategy, in addition to the following key community-engaging activities: the gift recipients will be invited to choose and keep one anonymously donated postcard, submit handwritten postcards of their own, draw on plain fans, and decorate with stickers, send out messages that encourage testing on social media platforms or create videos promoting gonorrhea testing (to be viewed at the same clinic). Men who agree to participate in the community engagement activities will be invited to a hybrid digital and in-person pay-it-forward event where they meet other people who have donated and to related participatory activities organized by the local clinic to promote gonorrhea testing.

Data collection

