We have developed an interview guide as part of formative testing. The main topics in the interview guide will include the following: (1) reasons for getting tested; (2) understanding and perception of the pay-it-forward concept; (3) specific questions about emotions of gratitude after receiving a test that is supported by another community member; and (4) self-identity in the MSM community and level of integration within a community; (5) intention and motivation to initiating and mediating helping behaviors within the community. We will obtain recorded verbal informed consent from all interviewees before the commencement of the interview. Interviews will last about one hour and will take place either in person or over the phone-based on participant preference.

Interviews will be audio-recorded, and personal information will not be recorded. Unintentional recording of personal information will otherwise be redacted before transcription. Each participant will receive a small monetary incentive of ¥50 (7.50 USD) for their participation. All recorded interviews will be transcribed, and the transcripts will be checked by one research staff member. Summaries of interviews will be written up for preliminary data analysis. In addition, we will collect anonymized text from handwritten postcards and other community engagement activities.

Pragmatic cluster RCT

Sample size and power considerations

We used a binary outcome cluster RCT design for sample size calculation where the unit of randomization is the clinic. In order to achieve a 90% power and allow for 0.05 type-I error, 12 overall clusters (4 in each arm) are needed. Thus, the sample size includes a total of 12 clusters and 1200 participants (100 per cluster) based on cluster randomized trial sample size calculation principles. We expect this study will have 85% power to detect a 10% difference in azithromycin resistance between intervention arms and routine gonorrhea antibiotic surveillance data from other cities in the same province. Nevertheless, further calculations will be made following formative research endeavors that will estimate the prevalence of these outcomes. The calculation would be performed using the software PASS (version 15) with the formulas developed by Hussey and colleagues.³⁶

Randomization

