Figure 2 shows the cluster RCT design flowchart. We will assign clinics to study arms on a 1:1:1 basis using covariate-constrained randomization. We will use covariate-constrained randomization to decrease potential bias associated with unbalanced study arms. We will balance the number of MSM-led and public clinics in each arm because these are unique implementation structures. All men recruited via one clinic will be assigned to one arm. We will recruit and screen men until we meet our sample size of 1200 men.

[figure not shown]

Figure 2. Pragmatic RCT flowchart. Each city will have one MSM-led clinic and one public clinic participating.

Intervention delivery strategies

The duration of the intervention is one year at each clinic, with the potential to continue based on local commitments. All patients who accept testing will receive gonorrhea/chlamydia PCR testing. This diagnostic is approved by the US FDA and the Chinese national regulatory authority. Men who agree to be tested will have specimens collected from

pharyngeal, rectal, and urethral sites. Specimens will be pooled based on excellent sensitivity and specificity. Turnaround time for test results will depend on the local clinic. Surveys will be done online in order to facilitate implementation. All participants diagnosed with gonorrhea will receive ceftriaxone and azithromycin in accordance with WHO recommendations for first-line gonorrhea therapy.

Outcome measures

The primary outcome of the RCT will be gonorrhea test uptake ascertained by administrative review from participating clinics. We used this same primary outcome in previous quasi-experimental and RCT trials evaluating pay-it-forward. Secondary outcomes will include syphilis testing, amount donated towards pay-it-forward, antimicrobial resistance measures, positive tests for gonorrhea and chlamydia, measures of gratitude and community solidarity, and per unit costs associated with the intervention (Table 2).

Table 2. Secondary outcomes of the cluster RCT			
Outcome	Time Frame	Ascertainment	Data Analysis
Primary			
Gonorrhoea and Chlamydia test uptake		Clinic administrative data	Generalized mixed effects models (compare control arm to pay-it-forward intervention)
Secondary			
Amount donated	During enrollment visit	Administrative data	Descriptive analysis
The number of participants who tested positive for Gonorrhea	During enrollment visit	Laboratory result	Descriptive analysis

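### Allocation is balanced on clinic type but the primary mixed model names no clinic-type term, nor the level of clustering it needs to be valid

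*Combined protocol and SAP*

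**What the plan says.** **Allocation.** Design overview: "Randomization will be based city economic status and stratified by clinic type". The Randomization section under Pragmatic cluster RCT adds: "We will balance the number of MSM-led and public clinics in each arm because these are unique implementation structures". Study setting and population gives the two types different entry rules: MSM-led clinics take only eligible MSM, while public clinics take all eligible men whatever their orientation.

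**Primary analysis.** The primary row of Table 2 reads "Generalized mixed effects models (compare control arm to pay-it-forward intervention". The Data analysis section repeats the model class and names two superiority comparisons. Neither place lists fixed covariates, random effects, a link or a method for degrees of freedom (df). Clinic type appears only among the subgroup analyses in Table 2.

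**Unit of randomization.** The sample size section describes a design "where the unit of randomization is the clinic". The abstract says: "The public and MSM-led clinics in the same city will be randomized to the same study group to prevent contamination". The Figure 2 caption gives every city one clinic of each type. With 12 clinics that means 6 cities, two per arm.

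**Size.** "In order to achieve a 90% power and allow for 0.05 type-I error, 12 overall clusters (4 in each arm) are needed". The inputs are left open: "further calculations will be made following formative research endeavors that will estimate the prevalence of these outcomes".

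**The concern.** A factor that is forced to balance across arms adds nothing to the sampling variability of the arm contrast. If the model leaves that factor out, its effect stays in the residual between-clinic variance and the reported SE is too large for the design. The confidence interval is then too wide, the test rejects too rarely under the null, and power is lost. With 12 clinics this can matter, because the variance is estimated from very few units. Different entry rules give reason to expect that uptake may differ by clinic type.

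The direction of the error depends on the unit of randomization. If both clinics of a city go to the same arm, a model that ignores city leaves out a real source of variance. The SE can then be too small.

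**Working it through.** **The plan's own figure.** The 90% power can be neither reproduced nor refuted, because control uptake, effect size and ICC are not given. Only 12 × 100 = 1200 can be checked.

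**Inputs.** From the documents: 12 clinics of 100 men, 3 arms, two clinics of each type per arm, alpha 0.05 (two-sided assumed). Everything else is assumed: uptake, ICC, its split between city and clinic, and D, the uptake difference between clinic types. Vclinic below includes binomial sampling variance. The formulas apply to clinic proportions.

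**1. Independent clinics, model without clinic type.**
- True variance of an arm contrast = Vclinic × (1/4 + 1/4) = Vclinic/2, whatever D is.
- Each clinic lies D/2 from its arm mean because of type. The extra residual sum of squares is 12 × (D/2)² = 3D² on 12 − 3 = 9 df, which adds D²/3 to the estimated variance.
- Example with uptake 35% and ICC 0.02: Vclinic = 0.02 × 0.2275 + 0.98 × 0.2275/100 = 0.00678, so the true SE = √(0.00678/2) = 0.058.
- At D = 10 points the model SE = √((0.00678 + 0.00333)/2) = 0.071, or 1.22 times the truth. The ratio is 1.06 at 5 points and 1.72 at 20 points.

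**2. Whole cities assigned, model ignores city.**
- True variance = (2Vcity + Vclinic)/2.
- Estimated without clinic type: (⅔Vcity + Vclinic + D²/3)/2.
- Estimated with clinic type: (¾Vcity + Vclinic)/2.
- Without the term, the SE is too large only if D²/3 > (4/3)Vcity, that is, D > 2 × the city SD. With the term, it is too small whenever Vcity > 0.
- Same example with half the ICC between cities: Vcity = 0.002275, Vclinic = 0.0045, true SE 0.067. The SE with clinic type is 0.83 times the truth. Without it, at D = 10 points, it is 1.02 times the truth, because two errors happen to cancel.

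**3. Whole cities assigned, city random effect.**
- Expected between-city mean square (6 − 3 = 3 df): Vclinic + 2Vcity, free of D.
- Expected within-city mean square without clinic type (6 df): Vclinic + 3D²/6 = Vclinic + D²/2.
- In the example at D = 10 points: 0.0045 + 0.0050 = 0.0095 within cities, against 0.0045 + 0.00455 = 0.0091 between. The estimated city variance is often pushed to zero, and the inflated within-city variance is pooled into the SE.

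**4. Simulated operating characteristics** (clinic proportions; assumed ICC 0.02, 40% v 60% uptake for power; ICC split equally between city and clinic in the whole-city rows).

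| Design and model | D | Without clinic type | With clinic type |
|---|---|---|---|
| Independent clinics, 9 / 8 df: power | 10 points | 71% | 82% |
| | 20 points | 35% | 82% |
| Whole cities, city random effect, 3 df: power | 10 points | about 35% | about 46% |
| | 20 points | 9% | 45% |
| Whole cities, city ignored: type I error | 10 points | 4.5% | 9.6% |

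At ICC 0.05 the last row becomes 8.1% and 11.2%.

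**5. Check with a logistic random-intercept model** (300 fits; no city effect, clinic SD 0.3 and type difference 0.8 on the logit scale, under the null). The mean model SE was 0.353 without clinic type and 0.220 with it, against an empirical SD of about 0.25. The mechanism carries over to the planned model class.

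**6. Cost when D = 0.** The critical t moves from 2.26 (9 df) to 2.31 (8 df). In a separate scenario (control uptake 25%, log odds ratio 0.8, clinic SD 0.3 logit, independent clinics) power moved from 80.5% to 79.3%, about 1 point. With a city random effect and 3 df there was no loss.

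**The case against.** **The plan does not exclude clinic type.** It is silent on every covariate. A reader might infer that the planned model contains only arm and clinic, so that its standard errors are too large and power is lost for nothing. The documents do not support that: no model without clinic type is stated, and the direction depends on the unit and level of clustering. Under the abstract's rule, a model that ignores city can be anti-conservative, and the added term then exposes the understatement. This stands, and it limits the point to a conditional one.

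**The type term cancels at city level.** In an analysis of city means, each city holds one clinic of each type. Power is then about 50% in the half-and-half split (about 60% with no city variance), essentially regardless of D. This is correct, but the protocol plans mixed models, where the term still matters (step 3).

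**The size is assumed.** The protocol says that the populations and settings differ, not that uptake differs by 10 or 20 points. At 5 points the SE ratio is only 1.06 with independent clinics. Where the error is conservative, it does not threaten a positive result. All of this stands.

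**City economic status is the other allocation factor and is equally unnamed.** True. It varies between cities, so if cities are assigned whole, a term for it would use one of only 3 between-city df. Clinic type varies within cities and does not.

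**Odds ratios.** In a logistic mixed model, adding clinic type also changes the conditional odds ratio, so standard errors with and without it are not strictly comparable on that scale. The calculations on proportions avoid this.

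**Conclusion.** The point holds as a gap in specification with a conditional consequence. The trial balances on clinic type, and the primary model as written does not name it. With independent clinics, or with city as a random effect, leaving it out makes the SE too large by an amount set by the type difference. Under the assumed values, a 10-point difference costs about 11 points of power in either case (82 − 71 and 46 − 35). If the types have similar uptake, nothing is lost.

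If cities are assigned whole and city is ignored, the SE can be too small, and clinic type alone does not repair it: type I error stays near 10% at ICC 0.02 with half of it between cities. The clinic-type term and the clustering level therefore have to be settled together. The 82% belongs to 12 independent clinics and should not be read as the power of the corrected analysis if cities are the unit.

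**What to change.** 1. Reconcile the abstract and the sample size section on whether the clinic or the city is randomized.
2. Prespecify the primary model with clinic type (MSM-led v public) as a fixed effect, clustering at the level actually randomized (city, if the abstract's rule applies) and a named small-sample df method.
3. State how city economic status is handled. A sensitivity analysis is reasonable if cities are the unit, given 3 between-city df.
4. When the deferred power calculation is made, base it on that unit and model, with stated uptake rates and ICC.

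The clinic-type term costs one line in the plan and at most one df, about 1 point of power if the types do not differ. It needs no new data, since clinic type is fixed by design. Moving to city-level clustering lowers the nominal power, but that follows from the allocation rule and not from the adjustment.
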